3.7 Subject Identification and Confidentiality

A study patient's medical record, including patient identification, will be made available for review by the study Sponsor, their representatives, and appropriate regulatory authorities. Any copies of medical records or eCRFs used to collect study data by the Sponsor will only identify patients by a unique patient identifier. Study results or information about the study that is made public will in no way disclose any patient's identity.

4. Study Procedures

The following sections outline the details of the clinical study methods for the Aortix CRS Pilot study. **Figure 1** summarizes the study design.

*Hemodynamic assessment can occur in the same procedure as the Aortix device implant. Patient must have urine collection device for at least 12 hours before implant.

Figure 1: Study Design Summary

Refer to **Appendix A: Schedule of Visits and Procedures** for detailed procedure schedule. For details on specific use of the Procyron Aortix System refer to the Aortix System Instructions for Use (PPL004).

4.1 Screening

Prior to consent, it is possible to review medical records to see if many of inclusion and exclusion criteria are present. If patients have worsening renal function and persistent congestion as defined in the inclusion/exclusion criteria, despite treatment with the institution's standard of care medical therapy, then he/she may be considered for the Study. During the study clinicians should avoid the use of nephrotoxic drugs. Prior to anatomical imaging and Swan-Ganz pulmonary artery catheter (PAC) placement, the patient will be evaluated for inclusion in the Study (pre-screening). If patient meets all other eligibility criteria, he/she will be approached for Informed Consent prior to final screening. Patients must sign informed consent before undergoing new PAC placement or study-related anatomical imaging assessments. Patients must be treated with optimal heart failure medical therapy per the institution's standard of care. Patients should be on intravenous diuretics for at least 48 hours before enrollment.

4.2 Enrollment

The patient is considered enrolled in the study when they sign the informed consent and before imaging screening is initiated. Following Informed Consent, imaging of ilio-femoral and aortic anatomy will be obtained to verify appropriate diameter and evaluate for any abnormalities that would preclude device placement. Imaging modality is up to the site, but one or more of the following modalities are recommended: non-contrast CT, intravascular ultrasound (IVUS) or external arterial ultrasound. Magnetic Resonance Angiography (without contrast) or CO2 angiography may also be considered.^x

If not done previously, PAC placement can occur any time after informed consent is signed and before device placement to confirm inclusion criterion for objective measure of congestion. Alternatively, PAC placement can occur in the cath lab before the Aortix device implant procedure.

4.3 Baseline Monitoring

Once patient is enrolled, baseline monitoring will begin. The following shall be done:

- Collect a medical history
- Perform a cardiovascular exam
- Collect vital signs (heart rate-HR, blood pressure-BP, respiratory rate-RR), NYHA classification, height
- Administer KCCQ and EQ5D assessments
- Collect baseline blood labs (See **Appendix A**).
- Echocardiogram (for the baseline echocardiogram, an echocardiogram taken during the current hospitalization may be used if the required parameters are recorded and no clinically significant changes are suspected from time of the echocardiogram to the baseline visit)

Echocardiogram parameters to be recorded: severity of AR, TR and MR, EF, LVESV, LVEDV, LVEDD, LVESD, CO, SV, LA diameter, TAPSE, and RVIDD. The selection of the echocardiogram technique and views are left to the

^x If the patient has had imaging within the last 12 months, this can be used in lieu of repeating the imaging if no clinically significant change is suspected.

institution. A report should be generated and kept as source documentation. Baseline assessments will be made in accordance with the schedule of assessments in **Appendix A**.

In addition to baseline monitoring, the following shall be done:

- Urinary collection device placement at least 12 prior to implant
 - Begin careful fluid intake and output (I/O) monitoring starting at least 6 hours prior to Aortix implant)
- Document current renal and cardiovascular medications
 - Cease to adjust diuretics and inotropes 12 hours prior to Aortix implant

The following categories of medications should be recorded, at a minimum: ACE inhibitor, ARNI, angiotensin receptor blocker, antiarrhythmic, beta blocker, digoxin, diuretic, inotrope, nitrate, MRA, SGLT2, thiazide diuretic, nitroprusside. Medication dose changes will be tracked through the 72 hour/discharge visit. Medications at the follow-up will also be recorded.

After signing informed consent, a urinary collection device will be placed, if not already present. A Foley catheter is recommended, but an external urine collection device may be used per institution requirements. The urine collection device will be placed (do not measure the urine collected during catheter placement) at least twelve (12 hours) before the Aortix Pump placement. If a urinary collection device is already in place, urine should be discarded. Output and intake should be strictly observed starting twelve hours prior to the scheduled implant. The urine collection device and the strict ins/outs monitoring will continue until the Aortix pump is retrieved. The first measurement of intake and output should occur at least six hours prior to Aortix placement and should be recorded every two hours until the pump is turned on. Measurements will occur at the frequency outlined in **Appendix A**.

Fluid ins should be monitored (IV and Oral) for the entire duration the urine collection device is in place with final measurements taken at the time of device retrieval.

Patients will receive standard medical therapy throughout the study. Patients should be on optimized medical therapy prior to being considered for Aortix Pump placement. To characterize the effect of the experimental device, physicians should not adjust the diuretic or inotrope dosing regimen during the twelve (12) hours prior to or the twelve (12) hours after Aortix Pump placement, unless medically necessary. **Diuretics and inotropes should not be adjusted for twelve (12) hours after the Aortix pump is turned on, however, after that point, while the Aortix pump is running, cessation of medications or down titration of diuretics, inotropes or other medications are allowed.** Adjustments of medical therapy can otherwise be made at any point during the study period at the discretion of the treating physician. All medications and medications adjustments will be captured on eCRFs.

4.4 Day of Implant

4.4.1 Pre-Implant

Prior to Aortix Pump placement, placement of a pulmonary artery (PA) catheter is required to confirm hemodynamic congestion inclusion criteria. In addition, patients should have a pulse oximeter for periodic oxygen

saturation (SaO₂) measurements. The following serial PA catheter measurements will be performed throughout the study per **Appendix A**:

- Central Venous Pressure (CVP)
- Pulmonary Artery (PA) Pressure Systolic
- Pulmonary Artery (PA) Pressure Diastolic
- Pulmonary Artery (PA) Pressure Mean
- Pulmonary Capillary Wedge Pressure (PCWP)
- SvO₂ (As measured on mixed venous gas from PA catheter)

On the day of the implant procedure, prior to the deployment of the Aortix device, the following assessments should be made (note: any baseline tests that were done on the day of implant do not need to be repeated and it is acceptable to enter the same data into the respective CRF):

- Cardiovascular exam (edema, pulmonary auscultation, weight)
- Vital Signs (HR, BP, RR)
- Dyspnea evaluation
- Fluid Ins and Outs
- Hemodynamics to include the following:
 - CVP
 - PA systolic
 - PA diastolic
 - PA mean
 - PCWP
 - SvO₂ as measured by the PA catheter
 - SaO₂ as measured by the pulse oximeter
- Blood and urine labs should be collected as per **Appendix A**.

4.4.2 Aortix Implant Procedure

Refer to the Aortix System Instructions for Use (PPL004) for all details of the Aortix Pump implant (deployment) technique, monitoring, management, and retrieval technique.

Anticoagulation should be initiated prior to the deployment of Aortix Pump in accordance with the Instructions for Use and **Appendix B: Anticoagulation Protocol**.

Ultrasound or another imaging modality should be used before and after implanting the pump to verify the femoral artery is not compromised (no vascular damage or clots).

Due to the potential for developing contrast induced nephropathy, if the use of iodinated contrast is required, then use the lowest dose possible and dilute 1:1 with saline.

Fluoroscopy should be used to aid in device placement and images of final device position should be captured and sent to Procyron.

If Aortix Pump is not positioned or functioning satisfactorily, the device may be repositioned or replaced as appropriate. After Aortix Pump implantation, anticoagulation should be maintained per **Appendix B**.

A fluoroscopic image of the final pump position should be taken, downloaded and the image documented. The image should be sent to Procyron.

During the procedure, patients should be monitored for any adverse events, including fever and anaphylaxis.

Any components of the Aortix Delivery System or Delivery Tool Kit that malfunction or are associated with an Adverse Event should be returned to the sponsor using the supplied Aortix Return Kit. Any device deficiencies should be reported.

4.5 Aortix Post-Deployment Monitoring and Management

The Aortix Pump has been tested to operate safely for 7 days of use. Aortix therapy should continue until objective signs of hemodynamic congestion have resolved, alternative / escalated therapy is required, or if device related safety concerns arise. The duration of Aortix pump use should be dictated by the physician's target for diuresis (net fluid and weight loss). In addition, the pre-specified target for pump effectiveness is a **minimum 20%** decrease in the patient's CVP and PCWP from pre-implant. **Diuretics and inotropes should not be adjusted for twelve (12) hours after the Aortix pump is turned on. After that point, while the Aortix pump is running, cessation of medications or down titration of diuretics, inotropes or other heart failure medications are allowed.** Adjustments of other medical therapy can otherwise be made at any point during the study period at the discretion of the treating physician. All medications and medications adjustments will be captured on eCRFs.

Refer to the Aortix System Instructions for Use (PPL004) for details of the Aortix Pump management.

If clinically significant device migration is suspected, use x-ray or another imaging modality to verify pump position.

It is recommended that the patient's vital signs be monitored frequently post procedurally (e.g., vitals checked every 15 minutes for the first hour, then every 30 minutes for the second hour). The patient's pedal pulses should be monitored post procedurally frequently for distal limb perfusion, ideally but not limited to, every fifteen (15) minutes times four (4), every thirty (30) minutes times two (2) and every hour (1) for two (2) hours and then as frequently as signs and symptoms warrant. In addition, the access site should be monitored for bleeding, hematoma, swelling or signs of infection.

Patients should be closely monitored during Aortix therapy and evaluated for any signs of vascular steal, including hearing loss, decrease in mental acuity, tinnitus, blurred vision, dizziness, vertigo, loss of muscle coordination, neurologic changes, or fainting. If any of these symptoms are observed, consider evaluating carotid circulation with doppler ultrasound and/or turning the pump speed down. In addition, report these signs as adverse events in accordance with Section 6. Since patient vital signs are monitored every 6 hours while the Aortix pump is implanted, it is recommended to evaluate the patient for signs of vascular steal while their vital signs are being monitored.

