4.5.1 Initial Data Collection

Following the implant procedure (time zero), the following data will be collected and entered on the eCRFs while the pump is implanted:

- Two (2) hours post implant:
 - Vital signs (HR, BP, RR)
 - Fluid Ins and Outs since last reading
 - Hemodynamics
 - CVP
 - PA Systolic
 - PA Diastolic
 - PA Mean
 - PCWP
 - SvO2 as measured by the PA catheter
 - SaO2 as measured by pulse oximetry
 - Document any medication changes and adverse events
 - Urine labs per Appendix A
- Six (6) hours post implant and every 6 hours for 24 hours post implant:
 - Vital signs (HR, BP, RR)
 - Fluid Ins and Outs since last reading
 - Hemodynamics
 - CVP
 - PA Systolic
 - PA Diastolic
 - PA Mean
 - SvO2 as measured by the PA catheter
 - SaO2 as measured by pulse oximetry
 - Document any medication changes and adverse events
- Twelve (12) hours post implant and every 12 hours until Pump retrieval:
 - Blood and urine labs per Appendix A
- Twenty-four (24) hours post implant and every 24 hours until Pump retrieval:
 - Cardiovascular exam (edema, pulmonary auscultation, weight)
 - Vital signs (HR, BP, RR)
 - Fluid Ins and Outs since last reading
 - Hemodynamics
 - CVP
 - PCWP
 - PA Systolic
 - PA Diastolic
 - PA Mean
 - SvO2 as measured by the PA catheter
 - SaO2 as measured by pulse oximetry

- Dyspnea evaluation
- Document any medication changes and adverse events
- Blood labs per Appendix A

BMI will be calculated by the sponsor. Patient should be maintained on anticoagulation and antiplatelet therapy per **Appendix B**.

If the Aortix Pump is suspected to be malfunctioning or mal-positioned, imaging studies, diagnostic procedures, or access site exam may be performed as needed.

Prior to any unplanned retrieval of the Aortix Pump, hemodynamic and laboratory assessments should be repeated, and a fluoroscopic image of the pump position should be taken, and the image documented.

Refer to **Appendix A** for a detailed study monitoring schedule.

4.5.2 Programming the Aortix Pump/Pump Speed Changes:

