Appendix A: Schedule of Visits and Procedures

Category	Pre-Therapy		Aortix Therapy								Post-Therapy			
	Pre-Implant Period (Baseline Monitoring)	Day of Implant (Pre-implant)	Implant to Pump Retrieval					Once Congestion Target is Met and Within 12 hours of Beginning Weaning ^α	Day of Pump Retrieval (Pre-Pump Retrieval)	Cath-Lab Pre-Pump Retrieval	Post-Pump Retrieval Monitoring		Follow-Up: 30 days (± 7 days) from Pump retrieval	
	Current hospitalization once	once	Once (after pump deployed)	2 hours post implant ⊕ (± 30 min)	6 hours post implant (± 30 min) and Every 6 hours (± 1 hour) for 24 hours post implant	Every 24 h (± 2 hours)◆	Pump Speed Changes #	once	once	once	Every 24 h (± 2 hours)	Once at 72 hours post retrieval (± 4 hours) or discharge (whichever is earlier)	once	
Informed Consent ¹	X													
Med History	X													
NYHA Class	X											X	X	
Cardiovascular exam (edema, pulm auscultation, weight)	X	X				X		X				X	X	
Vital Signs: HR, BP, RR #	X	X		X	X	X	X	X		X		X	X	
Height	X													
Fluid Ins and Outs*		X*		X	X	X	X	X		X	X ^β			
Dyspnea Evaluation		X				X		X				X	X	
KCCQ, EQ5D	X												X	
HEMODYNAMICS														
CVP, PAP #		X		X	X	X	X	X		X				
PCWP #		X		X		X	X	X		X				
SvO ₂ , SaO ₂ **		X		X	X	X		X		X				
IMAGING														
Anatomy Screening	X													
Echo	X							X						
Fluoro Image			X							X				
MEDICATIONS	X		Record all cardiovascular/renal medications and medication changes.****										X	
OTHER EVENTS***			Record all adverse events, readmissions and mortality.											

1 Patient must sign informed consent before undergoing PA catheter placement for verification of inclusion criteria for objective measure of congestion or before undergoing imaging to assess anatomy for exclusion criteria for contraindicated anatomy.

α One time assessments to be taken once congestion targets are met or therapy has been deemed ineffective (decision has been made to retrieve device). These assessments should be performed before the pump speed is turned down; within 12 hours of beginning weaning.

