* Urine collection device should be inserted at least 12 hours before pump implant. Urine collection device may be removed at time of pump retrieval. Urine output measurement should exclude volume collected as part of urine collection device placement procedure. Fluid ins should be monitored (IV and Oral) for the entire duration the urine collection device is in place with final measurements for UOP and fluids in at the time of removal of the urine collection device. The “Day of Implant (Pre-implant)” UOP measurements should be taken every 2 hours before the pump is turned on. The first measurement of intake and output should occur at least six hours prior to Aortix placement and should be recorded every two hours until the pump is turned on.

** Cardiac Output (CO) and Cardiac Power Output (CPO) will be calculated by the sponsor. CPO parameters to be collected: SaO₂ (as measured by pulse oximeter), SvO₂ (as measured on mixed venous gas from PA catheter), hemoglobin (from CBC), blood pressure (to calculate MAP), weight, height, and heart rate.

HR, BP, PCWP, CVP and PAP – these values should also be collected any time the speed of the pump is adjusted. For PCWP it should be within 2 hours (+/- 30 min) of a speed change. For HR, BP, CVP and PAP it should be within 1 hour (+/- 30 min) of a speed change.

*** For United States patients, hospital billing information will be collected post-patient discharge.

^β Data collection at this time point is optional. Urine Output and Fluids IN required post device retrieval ONLY if urine collection device is still in place.

**** All heart failure and renal medications/medication adjustments should be recorded from baseline to discharge/72 hours post-device retrieval (whichever is first). At the 30 day follow-up, current medications should be recorded. Medication changes between discharge/72 hours post-device retrieval and follow-up do not need to be recorded.

⌚ 2 hours from time pump turned on during the deployment procedure.

◆ First measurement should be made 24 hours after pump is turned on. Subsequent every 24 hour measurements can be made during daily rounds or another convenient time as long as the first every 24 hour measurement is made at least 12 hours after the initial measurement 24 hours after the pump is turned on.

Hemodynamics Data Collection

Category	Pre-Therapy		Aortix Therapy								Post-Therapy		

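### Section 4.5 links the vascular-steal check to 6-hourly vital signs throughout implantation, but the protocol schedules 6-hourly vital signs only for the first 24 hours

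*Protocol*

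**What the plan says.** Protocol Section 4.5 deals with vascular steal in two steps. It first gives a general instruction with no interval: "Patients should be closely monitored during Aortix therapy and evaluated for any signs of vascular steal". It then adds a practical recommendation: "it is recommended to evaluate the patient for signs of vascular steal while their vital signs are being monitored". The reason for this recommendation is put forward as fact: "Since patient vital signs are monitored every 6 hours while the Aortix pump is implanted". Any such signs are to be reported as adverse events under Section 6.

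Section 4.5.1 lists the data to be collected while the pump is in place. Vital signs appear at 2 hours and in two repeating blocks. The first is "Six (6) hours post implant and every 6 hours for 24 hours post implant" and the second is "Twenty-four (24) hours post implant and every 24 hours until Pump retrieval". Between them is a block headed "Twelve (12) hours post implant and every 12 hours until Pump retrieval", which contains blood and urine laboratory tests only.

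Appendix A agrees with Section 4.5.1. Its vital-signs row is marked in the column headed "6 hours post implant (± 30 min) and Every 6 hours (± 1 hour) for 24 hours post implant" and in the 24-hourly column. It is also marked at 2 hours, at pump speed changes, at the congestion-target timepoint and in the cath lab before retrieval. The footnote to the 24-hourly column says "First measurement should be made 24 hours after pump is turned on" and allows some latitude in the timing of later readings.

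**The concern.** Section 4.5 treats 6-hourly vital signs as an established feature of the whole implant period and attaches the steal check to them. After 24 hours the protocol schedules no such readings. A site that works from Section 4.5 would look for steal every 6 hours until retrieval. A site that works from Section 4.5.1 or Appendix A would reach a scheduled vital-signs check once a day from the second day.

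This link is the only interval stated anywhere for steal surveillance. Neither Section 4.5.1 nor Appendix A has a line for a steal or neurological assessment. Vascular steal is among the potential risks in Section 5.2, and several of the signs in Section 4.5, such as tinnitus, dizziness or reduced mental acuity, may come to light only if someone asks or examines. Section 4.5.2.1 allows pump speed to be raised after two days if targets have not been met, so any such increase falls in the period with the sparser schedule.

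What is at stake is even detection of milder steal symptoms between sites, and between the first day and later days. Such events would appear in the adverse event tables. If adjudicated as device-related, they would also count in the device-related event rate (Protocol 3.3.2, SAP 7.8.2), which is not restricted to serious events.

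**Working it through.** The plan states no figure for this point, so there is none to reproduce. The check is a comparison of passages followed by a count of timepoints.

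**Inputs**
- Interval assumed in Section 4.5: 6 hours, for as long as the pump is in.
- Interval scheduled in Section 4.5.1 and Appendix A: 6 hours up to hour 24, then 24 hours until retrieval.
- Shortest planned initial run at the starting speed: two days, or 48 hours (Section 4.5.2.1).
- Tested duration of pump use: 7 days, or 168 hours (Section 4.5).

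**Formulas**, for t hours of support with t a multiple of 24:
- 6-hourly throughout: t/6.
- As scheduled: 4 + (t − 24)/24, where the 4 are hours 6, 12, 18 and 24.

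Both counts leave out the 2-hour reading and all event-driven readings.

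| Support | 6-hourly throughout | As scheduled |
|---|---|---|
| 48 h | 48/6 = 8 | 4 + 24/24 = 5 |
| 168 h | 168/6 = 28 | 4 + 144/24 = 10 |

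The first 24 hours contribute 4 to each count, so the whole difference arises later. After hour 24 the counts are 8 − 4 = 4 against 5 − 4 = 1 by 48 hours, and 28 − 4 = 24 against 10 − 4 = 6 by 168 hours. In both cases the schedule gives one quarter of the regular checks that Section 4.5 presumes.

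**Adding the other fixed readings.** The 2-hour, congestion-target and pre-retrieval readings add at most 3, giving up to 5 + 3 = 8 at 48 hours and 10 + 3 = 13 at 168 hours. The totals are lower if timepoints coincide, since Section 4.5.3 lets a scheduled value serve as the congestion-target value. The match of 8 with 8 at 48 hours is one of number only. One added reading is at hour 2 and the other two belong to the end of therapy, so they do not make a 6-hourly series. Readings at speed changes add more, but a patient kept at constant speed has none of these between daily checks until weaning.

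**The case against.** The strongest reply is that the two places do different jobs. Section 4.5.1 lists what is entered on the case report forms, while Section 4.5 describes bedside care. Ward vital signs could be taken every 6 hours with only some recorded for the study. Section 4.5 already works this way for the first two hours, where it recommends far more frequent checks than the single 2-hour reading in the schedule. It also refers pump management to the Instructions for Use, which are not among the documents. This reading is possible and part of the fix allows for it. But the protocol does not say so, Section 4.5.1 points to Appendix A as the detailed monitoring schedule, and nothing in either document requires 6-hourly vital signs after day 1.

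The second reply is that steal surveillance does not depend on the premise. The general instruction covers all of therapy, and the check at vital signs is only recommended. That stands, and it limits the weight of the point. What remains is an instruction with no interval.

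A reader might go further and infer that the primary safety rates would differ between sites. The documents do not support that. Adverse events are to be reported until study exit (Section 6), whether or not they are found at a vital-signs round. Patients are in hospital and may report many of these symptoms themselves. Both primary safety endpoints count patients with serious events as classified by the clinical events committee, each patient once (SAP 7.8.1), so non-serious steal symptoms do not enter them.

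A reader might also take 28 against 10 as the typical gap. Seven days is the tested duration, not an expected one, and the count leaves out the event-driven readings.

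**Conclusion.** The contradiction is real: the premise in Section 4.5 holds for the first 24 hours and is contradicted by Section 4.5.1 and Appendix A from then on. With a planned initial run of at least two days, it reaches any patient treated as planned. On regular timepoints alone its size is 8 against 5 at 48 hours and 28 against 10 at 7 days. These are nominal counts that assume readings at the scheduled times.

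The consequence is modest. Detection of non-serious steal symptoms may be uneven between sites and over time on the pump. The documents give no basis for estimating by how much, and an effect on the primary safety rates is not shown. No endpoint definition, analysis population, sample size or test is affected. This is an internal inconsistency in a safety-monitoring instruction, worth correcting because it undercuts the one interval given for that surveillance.

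**What to change.** Reconcile Section 4.5, Section 4.5.1 and the vital-signs entries and footnotes in Appendix A in one of two ways:

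- state one frequency that applies to vital signs and to the linked steal assessment for the whole implant period, and use it in all three places; or
- say explicitly in Section 4.5 that it refers to bedside vital signs taken in addition to those on the case report form schedule.

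Which frequency to adopt is a matter for the clinical team, and this review proposes none. The second option costs wording only. The first also costs wording only, unless the agreed frequency changes what sites must record, in which case the case report form timepoints would need to follow.
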